We will present descriptive statistics for demographic and clinical variables, including by study group, but will not perform statistical comparisons of differences between study groups for baseline variables that should be balanced by randomization. We will first evaluate the primary outcome, the proportion of hearts transplanted, presenting the absolute and relative differences between the study groups, along with 97.5% one-sided confidence intervals. For our primary analysis, we will test the association between treatment and proportion of hearts transplanted, using a one-sided chi-square test at significant level of 0.025. Then we will proceed to a multivariate model that adjusts for potentially confounding variables and random site effect. The SRTR registry has developed comprehensive organ-specific risk-adjustment models (25). Older age and blood group are consistently the most important variables impacting whether hearts are transplanted. For this reason, we will include age and blood type as relevant pre-specified covariates. Since randomization was stratified by site, and imbalance in sample size across sites are expected, we will also include site as a random effects in our multivariate model. This will provide subject-specific measures of treatment effect, in terms of a conditional effect size and adjusted odds ratio (with 97.5% one bound confidence interval).

Given that a systematic assessment of non-randomized studies using T4 for heart donors has suggested an improved rate of hearts transplanted, while prior small randomized studies have suggested no effect (i.e. no studies suggesting that T4 therapy results in worse heart outcomes) (10), we have selected a superiority design as most appropriate for our primary outcome. We are seeking to ascertain whether the addition of T4 infusion to standard donor care results in more hearts transplanted. Therefore, our null hypothesis is that T4 treatment results in an equal or lower rate of hearts transplanted, meaning our alternate hypothesis is that T4 treatment is superior to no treatment. If the null hypothesis were not excluded, there would be no rationale to use T4 in addition to standard donor management and no benefit to focusing on a two-sided test evaluating whether it was worse than placebo. Therefore statistical tests will be one-tailed at a stringent significance

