level of 0.025. We will also present the effect size with confidence intervals for all outcomes. The analysis will follow an intention-to-treat model. However, we will also perform a secondary per-protocol analysis, including only those receiving at least six hours of study infusion. We will also analyze only those in the placebo group who did not receive open-label T4, for a secondary analysis.

We will analyze the primary safety endpoint of recipient graft survival using a non-inferiority method. Our baseline assumption, based on five-year data (from 2016 to 2020) provided by SRTR, is that 30-day graft survival for hearts will be 96%. We assume this baseline rate for both study groups, as there is no evidence to suggest that graft survival is lower in recipients of hearts from donors administered thyroid hormone. In fact, a recent study suggested treatment was associated with improved graft survival (23). The null hypothesis is that heart graft survival is lower in the T4 treated group by at least a clinically significant margin (set at 6%) compared with that observed in hearts transplanted from the placebo donors. This non-inferiority margin was selected with input of the data and safety monitoring committee (DSMC), including a thoracic transplant surgeon and ethicist. It aligns with that used in other trials assessing graft function after heart transplantation which used similar baseline assumptions (96% graft survival) but allowed more liberal margins (10%) (26). We believe that setting the lower limit of tolerance for this safety analysis at 90% graft survival is most appropriate. We will construct two-sided 95% confidence intervals for the difference in graft survival between the groups, allowing us to test for one-sided non-inferiority at alpha 0.025. This will be performed in the intention-to-treat cohort (i.e. all hearts from enrolled donors, by randomized study group) but we will also evaluate non-inferiority using a per-protocol methodology (i.e. evaluating outcomes in recipients who received hearts from donors who received at least six hours of T4 infusion compared to those who did not).

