Our plans for analyzing the secondary outcomes are as follows: for outcome measures that are time-to-event variables such as time to get off vasopressors and time to order first echo, we will perform Cox regression model to assess Hazard Ratio (95% confidence interval) between groups. We will calculate the vasopressor-inotrope score, VIS (27) as: $VIS = \text{dopamine dose } (\mu\text{g/kg/min}) + \text{dobutamine dose } (\mu\text{g/kg/min}) + 100 \times \text{epinephrine dose } (\mu\text{g/kg/min}) + 100 \times \text{norepinephrine dose } (\mu\text{g/kg/min}) + 10 \times \text{milrinone dose } (\mu\text{g/kg/min}) + 100 \times \text{phenylephrine dose } (\mu\text{g/kg/min}) + 10,000 \times \text{vasopressin dose } (\text{U/kg/min} - \text{only for doses } > 1 \text{ U/hour})$. We will compare the decrease in VIS from start of thyroid hormone or saline infusion until 12-hours (end of study infusion), using analysis of covariate method with predictor variables that include the baseline score and the treatment groups and adjusting for site effect. Cardiac ejection fraction will be evaluated using a linear mixed model adjusting for random site effect. If normality assumption is violated, data transformation will be performed. Count data regarding thoracic and total organs transplanted will be compared using Generalized Estimating Equations, with study group as the independent variable and expected organs transplanted as a covariate. All secondary outcome analyses will be two-tailed test at a significance level of 0.05.

Interim analyses {21b}

The DSMC statistician will perform one interim analysis when 376 donors have been enrolled with evaluable data. The trial may be terminated early if, based on the judgement of the DSMC, the interim findings

demonstrate either superiority or clear inferiority of T4 treatment compared to placebo (at a threshold of 0.01). The trial may also be terminated if there is inferiority of graft outcomes in either group, observed at 30-days in those hearts transplanted and observed for this period. The DSMC will provide recommendations to the study PIs, who will make final decisions about whether to stop or continue the trial.

Methods for additional analyses (e.g. subgroup analyses) {20b}

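### The primary outcome gets only one-sided intervals, so a non-significant result would not show whether the 10-point design effect is excluded; the primary test also omits the OPO strata, a smaller loss

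*Combined protocol and SAP*

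**What the plan says.** All references are to the combined protocol and SAP, v3.0.

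**Primary outcome.** Statistical methods {20a} plans on "presenting the absolute and relative differences between the study groups, along with 97.5% one-sided confidence intervals". The follow-on model, with age, blood group and a random site effect, reports an "adjusted odds ratio (with 97.5% one bound confidence interval"). The primary test is an unstratified one-sided chi-square at 0.025, with the null that T4 gives an equal or lower rate of hearts transplanted. In defence of one-sidedness the section says: "If the null hypothesis were not excluded, there would be no rationale to use T4 in addition to standard donor management", and sees "no benefit to focusing on a two-sided test evaluating whether it was worse than placebo".

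**Other outcomes.** For graft survival: "We will construct two-sided 95% confidence intervals for the difference in graft survival between the groups", used to test non-inferiority at one-sided 0.025. For secondary outcomes: "All secondary outcome analyses will be two-tailed test at a significance level of 0.05". A general sentence adds: "We will also present the effect size with confidence intervals for all outcomes". It does not say one- or two-sided, and it directly follows the statement that tests are one-tailed.

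**Interim.** Interim analyses {21b} allows early termination if the findings "demonstrate either superiority or clear inferiority of T4 treatment compared to placebo (at a threshold of 0.01"). Ethics approval {24} also provides for halting if one group has fewer hearts transplanted.

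**Design.** Sample size {14} sets 10 absolute points as the study's effect threshold (35% to 45%). Trial design {8} stratifies randomization by OPO, and the amendment history expects transplant rates to differ between sites. It also records that the chi-square was deliberately kept as the primary analysis.

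**The concern.** The protocol describes T4 as in common use at almost all OPOs (choice of comparators {6b}), and its own argument treats failure to reject as removing the reason to use T4. A non-significant result will therefore be read as a reason to stop. Whether it supports that reading depends on the upper limit of the difference. If that lies below 10 points, the design effect is excluded; if not, the trial is inconclusive about it. A lower-limit-only interval cannot make this distinction, and it cannot show that T4 lowers the rate, although the interim rules treat that finding as important. If the upper limit is added once the result is known, the choice of interval becomes post hoc.

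The second, smaller point is that the primary test does not use the strata in which donors were randomized. If transplant rates vary between OPOs, some precision is given up.

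**Working it through.** **1. The plan's sample size.** With p0 = 0.35, p1 = 0.45, mean 0.40, one-sided alpha 0.025 and 80% power:

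n = [1.960·√(2·0.40·0.60) + 0.8416·√(0.35·0.65 + 0.45·0.55)]² / 0.10² = (1.3579 + 0.5800)² / 0.01 = 375.6, so 376 per group and 752 in total, as stated.

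A two-sided 0.05 test also gives 376. At 400 per group, power is Φ[(0.10·√400 − 1.960·√0.48)/√0.475] = Φ(0.93) = 82.4%.

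**2. What single results would show.** Inputs: 400 per arm, 140 hearts (35%) in placebo. Difference d = p1 − p0; interval d ± 1.96·√(p0q0/400 + p1q1/400); p from the pooled z test.

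| Hearts, placebo vs T4 | d (points) | Planned display | Two-sided 95% interval | 10 points excluded? |
|---|---|---|---|---|
| 140 vs 153 | 3.25 | at least −3.4 | −3.4 to 9.9 | yes |
| 140 vs 160 | 5.0 | at least −1.7 | −1.7 to 11.7 | no |
| 140 vs 114 | −6.5 | at least −12.9 | −12.9 to −0.1 | yes; the interval lies below zero |

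For 140 vs 160: SE = √(0.35·0.65/400 + 0.40·0.60/400) = 3.42 points, 1.96·SE = 6.7, one-sided p = 0.072. On the ratio scales the upper limits are 1.37 for the risk ratio and 1.65 for the crude odds ratio. The design effect is a risk ratio of 0.45/0.35 = 1.29 and an odds ratio of (0.45/0.55)/(0.35/0.65) = 1.52, so both remain open.

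Against 140 placebo hearts, 153 is the largest T4 count with an upper limit below 10 points (154 gives 10.18). The smallest significant count is 167 (p = 0.0248). Counts of 154 to 166 are thus non-significant with 10 points still open.

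**3. How often each case arises.** Exact sums over both binomial distributions, 400 per arm, placebo 35%, pooled z test at one-sided 0.025, unpooled Wald upper limit:

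| True effect | Significant | Non-significant, upper limit < 10 | Non-significant, 10 open | Open among non-significant |
|---|---|---|---|---|
| 0 | 2.5% | 84.3% | 13.2% | 14% |
| 3 points | 14.2% | 54.2% | 31.6% | 37% |
| 5 points | 31.1% | 31.1% | 37.7% | 55% |
| 10 points | 82.2% | 2.4% | 15.3% | 86% |

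The last column is the fourth divided by the sum of the third and fourth, e.g. 13.2/(84.3 + 13.2) = 14%. The fourth column becomes 15.5, 35.0, 40.8 and 16.1% with placebo at 40%, and 15.4, 35.2, 41.4 and 17.6% with 376 per arm and placebo at 35%. These sums assume one analysis at full size and leave out stopping at the interim.

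**4. The strata.** The documents give no between-site SD, so a range on the logit scale was assumed. Simulation: 40,000 trials per setting, 14 sites of 22 to 98 donors (assumed; total 800), site-stratified blocks of 30, overall rates held at 35% and 45%.

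| Between-site SD | Chi-square power | Mantel-Haenszel power |
|---|---|---|
| 0 | 82.6% | 82.4% |
| 0.2 | 82.3% | 82.5% |
| 0.45 | 83.1% | 84.1% |
| 0.65 | 83.6% | 85.4% |
| 0.8 | 84.2% | 87.0% |

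Around a 40% rate, SD 0.45 puts 90% of sites between 24% and 58%; SD 0.8 puts them between 15% and 71%.

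Equivalent donors = 800·{[(z of MH power + 1.96)/(z of chi-square power + 1.96)]² − 1}: about 22 at SD 0.45 and about 69 at SD 0.8 (68 from the rounded powers). Under the null, the chi-square rejects in 1.9 to 2.6% of trials and Mantel-Haenszel in 2.4 to 2.6%. A second simulation with exact 1:1 balance within OPOs gave gains of 0.0 to 2.9 points for SD 0 to 0.8, and 4.0 at SD 1.0.

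**The case against.** **The interval is a reporting matter.** The test, alpha, sample size and lower limit do not depend on it. Any reader can compute the upper limit of the crude difference from the two counts. If the adjusted odds ratio has a Wald interval, its upper limit follows from the estimate and the lower limit. This stands: what is missing is the pre-specified interval, not the information.

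**The general sentence may already cover it.** The promise of intervals for every outcome does not rule out two-sided ones. But its sidedness is unstated, and it does not override the explicit one-sided wording for the primary outcome.

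**The one-sided display matches a one-sided design.** The plan's conclusion after a null result rests on failure to show superiority, and nowhere makes exclusion of 10 points a criterion. Graft survival and interim stopping serve different purposes, so the differences in sidedness are not contradictions. That is fair. Still, the graft-survival analysis shows that a two-sided interval sits easily with a one-sided 0.025 test.

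**The percentages do not measure harm done by the plan.** Correct: they are the chances of an inconclusive result at this sample size, whichever interval is printed. They also omit stopping at 376 donors, which does not change the conclusion.

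**The chi-square was deliberate and is adequate.** This also stands. It is valid and meets 80% power, and site enters the follow-on model. The gain from stratifying may be nil, and changing a primary test during an unblinded trial invites suspicion. This is why the second point carries less weight.

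**Conclusion.** The concern holds. As written, the primary report would leave open after every non-significant result whether 10 points is excluded, and it would show a reduction under T4 only as a lower limit. This is a gap in pre-specified reporting. It biases nothing and does not change the error rate or the power. It should be closed because a null result is expected to bear on common practice and, depending on the true effect, about one in seven to six in seven such results would leave the design effect open (placebo 35%, 400 per arm, single final analysis).

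The omission of strata is a modest forgone gain, not an error: about 0 to 3 points of power for an assumed between-site logit SD of 0 to 0.8, and nil if sites hardly differ. The text and the interval arithmetic are certain; the size of the strata effect depends on that assumed SD and on assumed site sizes.

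**What to change.** **Interval (main change).** State in {20a} that the absolute and relative differences and the adjusted odds ratio will be reported with two-sided 95% confidence intervals, keeping the one-sided 0.025 test. Add that a non-significant result will be described with the upper limit set beside the 10-point design effect. This guides interpretation and is not a new decision rule; excluding 10 points would still leave smaller benefits open. Cost: a sentence or two in the SAP. The lower limit, alpha and sample size do not change.

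**Test (secondary change).** Make the primary test Mantel-Haenszel stratified by OPO at one-sided 0.025, report the site-stratified risk difference, and keep the plain chi-square as a sensitivity analysis. The programming is minor, but recruitment began on 01 December 2020 and care is unblinded. The change must therefore be made without reference to outcomes by arm, dated, and recorded as before or after the interim (the documents do not say whether that has taken place). The estimate becomes site-weighted, with a mean absolute shift of 0.1 to 0.3 points in simulation, and at 35% vs 45% the two tests disagree on significance in 0.9 to 3.2% of simulated trials. If these conditions cannot be met, keep the chi-square as primary and name the stratified test as the first pre-specified supporting analysis.
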